6.6.2 Missing Safety Variables

Missing dates for occurrence of adverse events and non-study medication use will be imputed using the following rules:

1. Start dates with both missing day and month will be set to the 1st of January of that year, except as noted in rule 4 below. End dates with both missing day and month will be set to the 31st of December of that year.
2. Start dates with missing day only will be imputed with the first day of the month, except as noted in rule 4 below. End dates with missing day only will be imputed with the last day of the month.
3. Start dates with missing month only will be imputed by setting the month to January of the year. End dates with missing month only will be imputed to December of the year.
4. If a start date has missing day only with month and year the same as the month and year of the first dose date, then the start date will be set to the first dose date. If a start date has missing day and month with the year the same as the year of the first dose date, then the start date will be set to the first dose date.

If a start or end date are completely missing, then the date will be imputed with the dates of the first or last date of treatment, respectively. If an AE is ongoing (AEENRTPT= ONGOING) or a non-study medication is ongoing (CMENRTPT= ONGOING), the end date will be imputed by the end of study date (ADSL.EOSDT).

Missing data for all other safety endpoints will not be imputed.

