3.2 Schedule of Visits and Procedures Study

All subjects who are randomized and take any SM will be followed according to the protocol regardless of the number of doses of SM taken, unless consent for follow-up is withdrawn. [Table 1](#) below presents the Schedule of Visits and Procedures for the study.

Table 1: Schedule of Visits and Procedure

Period	Screening	Treatment Phase			
		Titration		Maintenance	
		Baseline, Randomization			End of Study ⁱ
Visit Number	1	2	3, 4	5-9	10
Visit Day		1	7, 14	21, 28, 35, 42, 49	56
Visit Window (days)	≤28d before V2		±2	±2	±2
Informed Consent/Accent (if applicable) ^a	X				
Medical and Psychiatric History	X				
Mini-KID	X				
Demographics	X				
Urine Drug Screen	X				
Randomization		X			
Physical Exam ^b	X				X ^c
Inclusion/Exclusion Criteria	X	X			
ECG (12-lead)	X				X
Vital Signs ^d	X	X	X	X	X
Hematology	X				X
Serum Chemistry	X				X

Pharmacogenomic sample	X				
Urine Pregnancy test, FOCP only		X			X
CGI-S	X	X			
CGI-I			X	X	X
C-SSRS	X	X	X	X	X
ADHD-RS-5	X	X	X	X	X
WFIRS-P, PSI-4-SF		X			X
Conners 3 ^e – parent, self		X			X
Concomitant Medication	X	X	X	X	X
Adverse Events		X ^f	X	X	X ^f
Drug Dispensed		X ^g	X	X	
Drug Return, Compliance			X	X	X
Optional PK Blood Sampling ^h			X	X	X

a To be obtained prior to performing any study procedures.

b Includes height and weight, excludes genitourinary system

c Changes from Screening only

d Seated (5 min) heart rate and blood pressure, temperature, respiratory rate

e Self report = 8-11 year olds only

f At Baseline, AEs are recorded only after SM is administered. Subjects with serious adverse events at EOS will be followed until the event has resolved or considered stable.

g Titration will begin after first dose of SM is administered

- ^h An optional PK substudy will take place between Visits 3 and 10, inclusive. Samples will be taken pre-dose and post-dose at Hours 1, 2, 4, and 6.
- ⁱ EOS or last visit in the case of early discontinuation.

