6.17.1.1 Treatment Emergent Adverse Events

A treatment-emergent adverse event (TEAE) is defined as an AE with a start date on or after the first dose of study drug is taken, or that worsened following first administration of study drug. TEAEs will be analyzed separately from those AEs that were not treatment-related. Only TEAE tables will be summarized. If a subject experiences more than 1 episode of a particular AE, the subject will be counted only once for that event. If a subject has more than 1 AE that codes to the same preferred term, the subject will be counted only once for that preferred term. Similarly, if a subject has more than 1 AE within a system organ class, the subject will be counted only once in that system organ class.

TEAEs will be summarized at the subject level by system organ class and preferred term for each treatment group in Table 14.3.1.2.

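### Rule 3 of SAP 6.6.2 moves an AE start date with only the month missing to January, without the first-dose safeguard of rule 4, so an on-treatment event can fail the TEAE definition

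*SAP*

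**What the plan says.** SAP 6.6.2 sets out four rules for partial dates and gives their scope: "Missing dates for occurrence of adverse events and non-study medication use will be imputed using the following rules". For start dates:

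- Rule 1 (day and month missing): "Start dates with both missing day and month will be set to the 1st of January of that year, except as noted in rule 4".
- Rule 2 (day missing): "Start dates with missing day only will be imputed with the first day of the month, except as noted in rule 4 below".
- Rule 3 (month missing): "Start dates with missing month only will be imputed by setting the month to January of the year". It has no reference to rule 4.
- Rule 4 substitutes the first dose date in two cases only. The first is "If a start date has missing day only with month and year the same as the month and year of the first dose date". The second is "If a start date has missing day and month with the year the same as the year of the first dose date".

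A start date that is missing altogether is set to the first date of treatment.

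SAP 6.17.1.1 makes an AE treatment-emergent if it starts on or after first dose, or if it worsens after first dose. On tabulation it says: "Only TEAE tables will be summarized". Under SAP 6.17.1 all AEs are listed in Listing 16.2.7.1 with a TEAE flag.

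**The concern.** Rules 1, 2 and 4, together with the provision for wholly missing dates, ensure that a partial start date compatible with on-treatment onset is not pushed before dosing. The month-only pattern is the one left outside that protection. The result is out of order: a date of which only the year is known is protected, while a date of which the day and year are known is not. Nothing in the SAP explains the difference, which looks like an oversight in drafting.

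At stake is the TEAE flag. A start date moved to January can take an on-treatment event out of the TEAE tables, which understates adverse events. That runs against the SAP's own approach to other missing AE data: missing severity counts as severe (6.17.1.2) and missing relatedness counts as definitely related (6.17.1.3).

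**Working it through.** The plan gives no figure on this point, so there is none to reproduce. The check applies the rules as written.

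**Step 1, the general case.** Suppose the first dose falls after 31 January of year Y and the AE start is recorded with its day and year Y but no month. Rule 3 gives a date in January of year Y, on 31 January at the latest. That is before first dose in every case. Neither part of rule 4 describes this pattern, so nothing corrects it.

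**Step 2, an example with illustrative dates.** First dose 1 October 2018, true onset 15 October 2018.

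| Missing part of start date | Rules | Imputed start | On or after first dose? |
|---|---|---|---|
| Day | 2 and 4 | 1 October 2018 | Yes |
| Day and month | 1 and 4 | 1 October 2018 | Yes |
| Whole date | Text after rule 4 | 1 October 2018 | Yes |
| Month | 3 | 15 January 2018 | No |

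**Step 3, how often this happens given the pattern.** Inputs: first dose on each of the 365 days of an illustrative non-leap year, and true onset on each of study days 1 to 58 (day 58 ends the Week 8 window in SAP Table 2). This makes 365 × 58 = 21,170 pairs. The uniform spread of dates is an assumption, as the SAP gives no enrolment calendar. Pairs with an imputed start before first dose:

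- Rules 1 and 4: 0 of 21,170.
- Rules 2 and 4: 0 of 21,170.
- Rule 3 as written: 18,616 of 21,170 = 87.9%.
- Rule 3 with the safeguard extended to it: 0 of 21,170.

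By month of first dose, the rule 3 rate is 49.9% for January, 100% for each month from February to October, 79.8% for November and 27.6% for December. It falls at the end of the year because an onset in the following calendar year is imputed to January of that year, which is after dosing. The range is therefore 27.6% to 100%, depending on when subjects were first dosed.

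All these percentages are conditional on the month alone being missing. None is a share of all AEs.

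**Step 4, from date to table.** An AE with a start before first dose fails the first part of the TEAE definition in 6.17.1.1. If it is not recorded as worsening after first dose, it fails the second part too and is not flagged as a TEAE.

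**The case against.** The strongest reply is that the rule will hardly ever be used. Table 1 collects AEs at Baseline and at each scheduled visit, about a week apart, over eight weeks of treatment. A recorded day and year with an unknown month is an odd gap in such data, and the likelier gaps are already covered. This stands, and it limits the weight of the point.

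Three stronger readings are tempting, and the SAP does not support them.

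- A reader might infer that every imputed pre-dose start must be wrong, because Table 1 footnote f says "At Baseline, AEs are recorded only after SM is administered". That footnote governs when AEs are recorded at Baseline, not when they began. The worsening part of the TEAE definition and the TEAE flag in the listing both allow for AEs that began before dosing.
- A reader might infer that a misdated event is certain to lose TEAE status. Only the pre-dose date is certain, under the conditions of Step 1. An event recorded as worsening after first dose still qualifies.
- A reader might infer that the event disappears from all AE reporting. It stays in Listing 16.2.7.1, and the SAE and death listings are not limited to TEAEs. Several tables are also described as covering AEs rather than TEAEs (14.3.1.1, 14.3.1.5 and 14.3.1.6), so the wording on tabulation is not uniform.

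Two objections concern the remedy. Substituting the first dose date discards the recorded day. That is true, and it affects the study day and duration shown in the listing, but TEAE status is what the safeguard protects. The rules also cover non-study medication, whose start may truly precede dosing. That stands too, so the remedy should be limited to AEs.

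None of this supplies the missing safeguard. No other part of the SAP covers the month-only case.

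**Conclusion.** The point holds as a gap in a stated rule. In the first-dose year, with first dose after January, rule 3 always dates a month-only-missing AE start before dosing. Unless worsening after first dose is recorded, the event fails the TEAE definition and may be left out of the TEAE tables.

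The practical size is very small. The pattern is rare, its frequency cannot be derived from the SAP, and 87.9% should not be read as a rate of lost events: it is conditional on the pattern and on an assumed enrolment calendar. Efficacy results are not affected. The point is a minor improvement, worth making because the error is non-conservative for safety and easily removed.

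**What to change.** Add to rule 3 the same cross-reference to rule 4 that rules 1 and 2 carry, and extend rule 4 for adverse events. The start date is set to the first dose date if all of the following hold:

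- only the month is missing;
- the year equals the year of first dose;
- the January date given by rule 3 falls before first dose;
- no recorded end date shows that the event ended before first dose.

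The rule for non-study medication starts need not change.

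The cost is one sentence in the SAP and about one line of code in the AE dataset derivation. Made before database lock, it spares the programmers a choice between applying a rule that drops an on-treatment event and departing from the SAP with a justification in the study report.

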2.1 Primary Objective

- To evaluate the efficacy of SPN-812 extended release (ER) compared to placebo as monotherapy for the treatment of ADHD in children (6 -11 years).

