6.9 Concomitant Medications

Concomitant medications will be assigned an 11-digit code using the World Health Organization Drug Dictionary (WHODD version 20170901 (Classic) Format B3) drug codes. Concomitant medications will be further coded to the appropriate Anatomical-Therapeutic-Chemical (ATC) code indicating therapeutic classification. Concomitant medications will be presented for each treatment period during which the medication was taken (Titration period, Maintenance period, and combined Titration and Maintenance period). A tabular summary of concomitant medications by drug class will be presented for the safety population in Table 14.1.2.4.

A subject data listing will be provided to include the reported medication name, the WHODD drug codes, ATC codes, study day and pertinent subject information (Listing 16.2.4.8).

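### SAP 6.6.2 can impute a medication start date that falls after the medicine's own recorded stop date, because three of its start-date rules never look at the stop

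*SAP*

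**What the plan says.** Section 6.6.2 opens with its scope: "Missing dates for occurrence of adverse events and non-study medication use will be imputed using the following rules". Adverse events and medications therefore share the same rules.

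The start-date rules are:

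- Day and month missing: "Start dates with both missing day and month will be set to the 1st of January of that year, except as noted in rule 4".
- Day only missing: "Start dates with missing day only will be imputed with the first day of the month, except as noted in rule 4 below".
- Month only missing: "Start dates with missing month only will be imputed by setting the month to January of the year". No exception is attached to this one.
- Rule 4, the exception, moves the start to the first dose date in two cases. One is a missing day with month and year equal to those of first dose. The other begins "If a start date has missing day and month with the year the same as the year of the first dose date".
- Start wholly missing: "If a start or end date are completely missing, then the date will be imputed with the dates of the first or last date". An unknown start therefore becomes the first treatment date.

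Three other places bear on how the imputed date is used:

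- Section 6.9 says "Concomitant medications will be presented for each treatment period during which the medication was taken", and names titration, maintenance and the two combined. It gives no date algorithm. It also requires study day in Listing 16.2.4.8.
- Section 6.2 starts the titration period on the first dose date and ends it at Visit 5.
- Table 1 in Section 3.2 records concomitant medication from Screening, up to 28 days before Visit 2. Footnote f has adverse events recorded at Baseline only once study medication has been given.

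**The concern.** Moving an unknown start to the first dose date suits adverse events. They are recorded only after dosing, so Day 1 is the earliest plausible start and counts the event as treatment-emergent.

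Medications differ. Because they are collected from Screening, the log can hold a medicine that ended before the first dose. If its start is unknown in one of the three ways listed, the rule overrides something the record does establish, namely that the medicine had already stopped. The derived interval then runs backwards.

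At stake are the derived medication dates, the study day shown in Listing 16.2.4.8, and possibly the period counts in Table 14.1.2.4. Section 7 requires all derived datasets to be programmed independently as well. With no check on date order and no stated period algorithm, two programmers could each follow the SAP and produce different versions of that table.

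**Working it through.** The plan states no figure to reproduce, so the check applies the start-date rules literally to test records.

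**Inputs.** The rules are those of Section 6.6.2. The titration period runs from first dose to Visit 5 (Section 6.2). For illustration, first dose is 15 Oct 2018 and Visit 5 is Day 21, which is 15 Oct + 20 days = 4 Nov 2018. These calendar dates are assumptions; the logic does not depend on them. UN marks an unknown part of a date.

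**Tests on each record.**

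- Backward interval: imputed start > recorded stop.
- Titration entry by start date alone: first dose ≤ imputed start ≤ Visit 5.
- Titration entry by overlap: imputed start ≤ Visit 5 and stop ≥ first dose.

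| Recorded start | Recorded stop | Imputed start | Start after stop? | Titration by start alone? | Titration by overlap? |
|---|---|---|---|---|---|
| wholly missing | 5 Oct 2018 | 15 Oct 2018 | yes | yes | no |
| wholly missing | 1 Mar 2016 | 15 Oct 2018 | yes | yes | no |
| UN-Oct-2018 | 5 Oct 2018 | 15 Oct 2018 | yes | yes | no |
| UN-UN-2018 | 30 Jun 2018 | 15 Oct 2018 | yes | yes | no |
| UN-Sep-2018 | 5 Oct 2018 | 1 Sep 2018 | no | no | no |
| UN-UN-2017 | 5 Oct 2018 | 1 Jan 2017 | no | no | no |
| 10-UN-2018 | 5 Oct 2018 | 10 Jan 2018 | no | no | no |

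**Study day.** Section 4 adds 1 on or after the reference date and adds nothing before it. For the first record, the imputed start gives 15 − 15 + 1 = Day 1, while the stop gives 5 − 15 = Day −10. The medicine would start on Day 1 and stop on Day −10.

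**Reading the table.**

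- All four records that meet one of the three triggering patterns have a backward interval. This follows from the text alone.
- The three records with other partial patterns are sound: their imputed starts precede the stops, and neither method places them in titration.
- Whether the four records enter titration depends on a step the SAP does not state: 4 of 4 by start date alone, 0 of 4 by overlap.
- The 2016 and June 2018 stops fall before the screening window, and the SAP does not say whether the log holds medicines that old. The point does not need them. A stop on 5 Oct 2018 lies within 28 days of first dose and triggers the fault under all three patterns.

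**After a fix.** If first dose is used only when the stop is missing or on or after first dose, none of the four records gets a Day 1 start, and none enters titration under either method.

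**The case against.** The strongest reply is that Section 6.9 already answers the question of consequence. It tabulates a medicine in the period in which it was taken, and a medicine with a stop before first dose was not taken in titration. A programmer who follows that wording uses both dates and counts none of these records. Section 6.1 leaves dataset specifications to be developed, so start-date assignment is not planned either. Section 6.1 also lists all eCRF data, so the true stop should remain visible. How prior medicines are defined is commonly left to the protocol.

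Much of this stands. It makes the false titration entry conditional, and a separate prior-medication class need not be demanded of the SAP. It does not remove the backward interval, which Section 6.6.2 produces whichever period method is used.

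A reader might infer three larger consequences that the document does not support:

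- *That the monotherapy claim is weakened.* No efficacy model in Sections 6.13 to 6.14.2 uses medication dates. The outputs concerned are a descriptive table and a listing.
- *That children could be given a false deviation and lost from the per-protocol set.* Section 6.5 has deviations documented and major ones finalized before lock. Nothing there derives them from dates imputed under 6.6.2.
- *That a sizeable number of children is affected.* The SAP gives neither how many medicines stop before dosing nor how often their starts are unknown in these patterns, so any count would be guesswork.

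**Conclusion.** The point holds as a minor correction. In three defined cases Section 6.6.2 gives a medication that ended before first dose a start later than its recorded stop. This is a stated rule producing an impossible result, not a detail left out.

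- **Certain from the text:** the backward interval, for every such record.
- **Conditional:** a wrong study day in Listing 16.2.4.8, if study day is derived from the imputed start.
- **Conditional:** a false Titration-period entry in Table 14.1.2.4, if periods are assigned by start date alone. Under overlap of start and stop there is none.
- **Not affected:** other partial start dates, and the primary and secondary efficacy analyses.

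The conclusion assumes that the medication log holds at least some medicines stopped between Screening and first dose, which the Table 1 collection schedule allows. Their number cannot be derived from the SAP.

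**What to change.** In Section 6.6.2, add for non-study medication only: *The first dose date is imputed as the start only if the end date is missing, ongoing, or on or after first dose. Otherwise the imputed start may not be later than the recorded end date.*

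One way to meet the second sentence is to let rules 1 and 2 apply without the rule 4 exception and to set a wholly missing start equal to the end date. In the test records this gives 1 Oct 2018 for UN-Oct-2018, 1 Jan 2018 for UN-UN-2018, and the stop date itself for the two wholly missing starts. None falls after its stop.

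In Section 6.9, add: *Period assignment uses both start and stop dates, so a medicine that ended before first dose is counted in no treatment period.*

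The cost is these few sentences and one start-not-after-stop check in the dataset derivation. Adverse-event handling does not change.

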6.7 Demographic and Baseline Characteristics

Demographic/baseline variables include age, age group, sex, ethnicity, race, height and weight at screening, and BMI. Baseline disease characteristics include ADHD-RS-5 total score, inattention subscale score and hyperactivity/impulsivity subscale score. Both will be summarized for the ITT population in Table 14.1.2.1 using descriptive statistics for continuous variables and using counts and percentages for categorical variables.

All demographic and baseline characteristics will be included in the subject data listing among all randomized subjects (Listing 16.2.4.1). The analysis populations will be listed in Listing 16.2.4.2.

Baseline comparability among the treatment groups will be presented in Table 14.1.2.2 using a chi-square test for the categorical variables, and using an F-test for the continuous variables. These p-values will be used for descriptive purposes, and will not be considered as the formal basis for determining factors to be included in statistical analysis model.

Mini-KID data will only be listed (Listings 16.2.4.3.1 and 16.2.4.3.2).

6.8 Medical and Psychiatric History

Medical history will be coded using MedDRA version 20.1. All medical and psychiatric history will be listed. Medical and psychiatric history will be summarized by body system for each treatment group in Table 14.1.2.3 for the safety population. The table will be sorted in alphabetic order by system organ class and the statistics n and % will be presented by treatment where: n is the number of subjects who present at least one occurrence of the medical history, and % is the percentage of subjects. The denominator used for calculating the percentages will be the total number of subjects included in the safety population in each treatment group. The tables will include two (2) parts: is the condition still active at screening (part a) or not (part b).

The pregnancy test results and urine drug screen will be listed in Listings 16.2.4.4.1 and 16.2.4.4.2. The medical history will be listed in Listings 16.2.4.5 - 16.2.4.7.

6.9 Concomitant Medications

Concomitant medications will be assigned an 11-digit code using the World Health Organization Drug Dictionary (WHODD version 20170901 (Classic) Format B3) drug codes. Concomitant medications will be further coded to the appropriate Anatomical-Therapeutic-Chemical (ATC) code indicating therapeutic classification. Concomitant medications will be presented for each treatment period during which the medication was taken (Titration period, Maintenance period, and combined Titration and Maintenance period). A tabular summary of concomitant medications by drug class will be presented for the safety population in Table 14.1.2.4.

A subject data listing will be provided to include the reported medication name, the WHODD drug codes, ATC codes, study day and pertinent subject information (Listing 16.2.4.8).

